8 EXPLORATORY ENDPOINTS

Several measures of efficacy in reducing respiratory morbidity in the short and long term will be explored. The trends and effects observed in this study will be used to determine appropriate efficacy outcome variables and the numbers of infants that would be required to be enrolled in a larger Phase 2 or Phase 3 study.

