8.1 Primary Endpoint: Long Term Efficacy – 12 months

The primary outcome of the study will be survival without CRM through 12 months CGA as measured by a validated respiratory diary based scoring system (presence of wheezing and/or coughing 2 days per week for 3 consecutive weeks) and pulmonary questionnaires (decrease in respiratory illness requiring medications, unscheduled medical visits and/or ER or hospital admissions) which have been shown to correlate closely with abnormalities on pulmonary function testing. The 12 month CGA endpoint has been shown to be more predictive of respiratory morbidity at two years of life than a diagnosis of BPD at 36 weeks CGA in previous studies of high frequency oscillatory ventilation in preterm infants.

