Power Analysis: A total of 88 preterm infants will be randomized to placebo, lower dose, or higher dose rhCC10 with an allocation ratio of 2:1:1. The primary analysis will be the comparison of placebo versus both rhCC10 dose groups combined. The prior trial demonstrated that the two doses are likely to yield similar results. Two doses will be used for the purpose of extending the safety profile for each individual dose, as that safety data may facilitate the choice of dose for a future Phase III confirmatory study. For SAEs or AEs with background rates of 5%, 10%, or 15%, the sample size of 22 in either dosing group will provide a probability of observing it of 68%, 90%, and 97%, respectively. The proposed trial is powered for the comparison of the two doses combined versus placebo for the composite endpoint of death or development of CRM. Secondarily, the study will yield effect size estimates for each individual dose versus placebo. Our assumptions regarding the comparison of placebo versus rhCC10 are based on the previous study with 7 placebo, 8 lower dose, and 7 higher dose infants (one infant in each of the rhCC10 treatment groups died). It is important to address the combined endpoint of death or re-admission to the hospital for respiratory problems. In the previous study, one loss-to-follow-up occurred in each of the three experimental groups and one death occurred in each of the rhCC10 groups. At 6 months, 3 of the 6 infants on placebo with follow-up were re-admitted to the hospital for respiratory problems and none of the 11 subjects treated with either rhCC10 dose with follow-up data were re-hospitalized. A realistic and conservative assumption for the 3 lost-to-follow-up babies is that they all either died or had respiratory disease. Then the proportions with disease or death on placebo and rhCC10 are assumed to have been 0.57 and 0.27. If the proportions in the proposed study are similar, with 44 subjects on placebo and 44 subjects in the two dose groups combined, power will be 82% with $\alpha=0.05$. nQuery Advisor version 6 was used.

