Data will be summarized for the total cases and by treatment group with respect to: 1) baseline demographic and clinical characteristics and 2) efficacy and safety observations and measurements. Analyses will be conducted on both the intention-to-treat (ITT) and 'per protocol' cases. Between-treatment or between-group comparisons will be examined using chi-square tests (or Fisher's Exact tests when cell frequencies are small) for categorical outcomes and Student t-tests (alternatively, Wilcoxon Rank Sum Test) for scalar measures. Two-sided statistical tests will be conducted and the significance level will be set at 0.05 for each primary test. The efficacy and safety analyses will be conducted on both the ITT and per protocol population. ITT cases will be all randomized subjects who receive the study medication, while per protocol cases will be randomized subjects who complete the study (including all cause deaths) without any major deviations from the protocol procedures. Descriptive statistics will be used to detail the sample characteristics. Between-treatment arm

differences on key baseline demographic and clinical characteristics will be tested. This latter step will be used to identify potential pre-treatment covariates for subsequent secondary analyses. Key baseline variables include race, gender, length, weight, head circumference, SNAPPE-II score, and gestational age. Descriptive statistics for the total exposure to study drug during the treatment period (number of doses), timing of initial study dose, timing of discontinuation in the event of early termination, and rate of study dropout will be provided. Between-treatment differences will be tested using the statistical methods described earlier. Concomitant medications will be summarized by therapeutic/pharmacological class and treatment group. In addition, they will be listed by treatment group, name of drug, dates administered, dose, frequency and indication.

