Efficacy evaluation: If CC10 is more efficacious than placebo, the CC10 treatment groups will have a higher rate of survival without BPD at 36 weeks CGA and/or survival without CRM at 12 months CGA (we are exploring which of these factors are more accurate predictors of long term respiratory morbidity). A 2 x 2 chi square test will be conducted to examine treatment differences in this binary endpoint and Kaplan-Meier survival curves will be constructed and any differences between the treatments will be tested using a Cox Proportional Hazards Regression Model. Secondly, a logistic regression will be employed to further detail the main and interaction effects of treatment and centers on the primary outcome. Odds Ratios (OR) with 95% confidence intervals (CI) will be provided. Subjects who die from respiratory causes before 12 months CGA will be considered treatment failures in both the ITT and per protocol analyses, and the last observation carried forward (LOCF) imputation method will be applied for early dropouts. For those subjects without diary data at any time point, respiratory status will be estimated based on available data during the follow-up period, including O₂ challenge test, pulmonary questionnaires, and use of asthma medications.

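### LOCF for early dropouts can only miss later failures on an endpoint counted through 12 months CGA, its fit with the no-diary rule is unstated, and no planned analysis varies the outcome of lost infants; the effect is modest

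*Combined protocol and SAP*

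**What the plan says.** Section 8.1 defines the primary outcome as "survival without CRM through 12 months CGA as measured by a validated respiratory diary based scoring system", supplemented by pulmonary questionnaires. The efficacy text of section 8.5 instead refers to survival without CRM at 12 months CGA, and tests it with a 2 x 2 chi-square.

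Section 8.5 then gives two missing-data rules in succession:

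- For infants who leave early: "the last observation carried forward (LOCF) imputation method will be applied for early dropouts".
- For infants lacking diaries: "For those subjects without diary data at any time point, respiratory status will be estimated based on available data during the follow-up period", the sources being the O₂ challenge test, questionnaires and asthma medications.

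Three planned elements handle lost infants in another way:

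- The per-protocol set leaves out non-completers: "per protocol cases will be randomized subjects who complete the study (including all cause deaths) without any major deviations from the protocol procedures".
- Dropout is described ("rate of study dropout will be provided") and compared between treatments.
- A time-to-event analysis is planned: "Kaplan-Meier survival curves will be constructed and any differences between the treatments will be tested using a Cox Proportional Hazards Regression Model". No censoring rule is given.

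The power analysis in section 8.5 treats lost infants differently again: "A realistic and conservative assumption for the 3 lost-to-follow-up babies is that they all either died or had respiratory disease". Section 8 states the purpose of the results: "The trends and effects observed in this study will be used to determine appropriate efficacy outcome variables", and the size of a later trial.

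**The concern.** **Direction of error.** If the endpoint runs through 12 months, an observed failure stays a failure whatever happens next. A CRM-free status at last contact is either right or misses later CRM or death. LOCF therefore pushes each arm's failure rate down. If the endpoint is status at 12 months, a CRM-positive status carried from an earlier assessment could also be wrong, and the net direction is no longer fixed.

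**Unresolved rules.** The phrase about diary data in the second rule can mean no diary at all, or no diary at a given time point. An infant with the 5-6 month diary but no 12-month diary goes to LOCF on one reading and to estimation on the other. An infant lost before 5 months has no diary status to carry and could fall under either rule. The plan does not say whether LOCF carries a diary, a questionnaire, a monthly call or the O₂ challenge. Two analysts could score the same infant differently on the primary endpoint. The O₂ challenge would be a weak substitute: section 2.1 reports that the BPD definition predicted CRM correctly only 35-40% of the time.

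**No check on the assumption.** The planned analyses could signal a problem with loss, but they would not show how far the result depends on what happened to the lost infants. At stake are the absolute failure rates and the risk difference passed on to the next trial.

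**Working it through.** **1. The plan's own figure.** Inputs from section 8.5: 44 v 44, failure 0.57 v 0.27, two-sided 0.05. The pooled-variance normal approximation gives 82.5% and exact enumeration of the Pearson test 82.6%. The stated 82% reproduces.

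**2. How the pilot loss was scored.** Sections 2.5.1 and 8.5 give 7 placebo and 15 rhCC10 infants, 3 placebo re-admissions, 2 rhCC10 deaths, and losses of 1/7 and 2/15.

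- Lost = failure: (3+1)/7 = 0.57 and (2+2)/15 = 0.27, difference 30.5 points.
- Lost = CRM-free: 3/7 = 0.43 and 2/15 = 0.13, difference 29.5 points.

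The choice moves both rates by 13 to 14 points but the difference by only 1 point.

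**3. Shrinkage with equal loss.** The documents give no expected loss for this trial, so I assume d = 1/7 per arm, unrelated to outcome. Let m be the share of lost infants' failures that go unseen. Under LOCF the observed rate is p(1 − d·m). Take 0.57 and 0.27 as true rates for illustration. Next-trial size per arm, two-sided 0.05 and 90% power, is

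n = [1.960·√(2p̄(1−p̄)) + 1.282·√(p₁(1−p₁)+p₂(1−p₂))]² / (p₁−p₂)².

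For 0.57 v 0.27: (1.960 × 0.698 + 1.282 × 0.665)² / 0.09 = 54.8, so 55.

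| Scoring of lost infants | Rates | Difference (points) | n per arm |
|---|---|---|---|
| True status | 0.570 v 0.270 | 30.0 | 55 |
| LOCF, half of failures seen (× 13/14) | 0.529 v 0.251 | 27.9 | 63 |
| LOCF, none seen (× 6/7, upper bound) | 0.489 v 0.231 | 25.7 | 72 |
| All missing = failure (p × 6/7 + 1/7) | 0.631 v 0.374 | 25.7 | 78 |

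The shrinkage under LOCF is 2.1 to 4.3 points. The 95% interval half-width at 44 per arm is 1.96·√[(0.57·0.43 + 0.27·0.73)/44] = 19.6 points.

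**4. False positives with no drug effect.** Exact Pearson rejection rate, 44 v 44, common failure rate 0.50 to 0.57. The unequal loss rates are assumptions.

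| Loss, placebo v rhCC10 | None seen before loss (upper bound) | Half seen |
|---|---|---|
| 1/7 v 2/15 (pilot) | 4.5-4.9% | – |
| 10% v 20% | 7.5-7.6% | 5.2-5.3% |
| 10% v 25% | 11.1-11.7% | 6.0-6.2% |

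A completers-only test under the same unequal but random loss stays at 5.0-5.2% (200,000 simulations), so divergence from the LOCF result would be a signal. The dropout comparison would itself be significant in 27% (10% v 20%) or 48% (10% v 25%) of trials.

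**5. Tipping illustration.** A result of 25/44 v 12/44 gives p = 0.005. With about six lost per arm (44/7 = 6.3), a net excess of four added rhCC10 failures gives p = 0.054 to 0.055 (25 v 16, 26 v 17, 27 v 18). If loss is unrelated to outcome, an excess of four or more has probability 0.07% at the planned rates and 1.8-1.9% with no drug effect. Scoring all six in each arm as failures (31 v 18) leaves p = 0.005.

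**The case against.** The strongest reply is that the harm is small and not peculiar to LOCF. Most of that stands.

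- **Sizing.** Scoring all missing infants as failures shrinks the difference to the same 25.7 points and asks for 78 per arm, more than LOCF's 72. On the pilot data the direction reverses: 4/7 v 4/15 needs 53 per arm at 90% power and 3/7 v 2/15 needs 47. A reader might infer that LOCF in particular will mis-size the next trial, or that the stated power is wrong. The documents support neither.
- **False positives.** A reader might infer that LOCF manufactures a benefit. That needs clearly more loss on rhCC10. A single blinded dose and pilot loss of 1/7 v 2/15 give no sign of it. The upper bounds also assume that no failure is seen before loss, although admissions, medical visits and medications are reviewed about monthly (section 6.4) and count toward the endpoint (section 8.1).
- **Existing safeguards.** The per-protocol set, the dropout comparison and Kaplan-Meier/Cox, which would normally censor lost infants, already treat them differently. Unequal loss would not necessarily pass unnoticed.
- **Exploratory status.** Section 8 labels the endpoints exploratory. That lowers the stakes, but the plan still sets a primary outcome, a power calculation and a 0.05 test.
- **Fragile imputation.** With roughly 12 infants lost among 88 at the pilot rate, any imputation model must be kept simple.

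What the reply does not answer: the stated rule biases the failure rates on section 8.1's wording, the two missing-data rules are not ordered, and nothing varies the outcome assumed for lost infants.

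**Conclusion.** The point holds in a limited form and should be corrected. On the through-12-months wording, carrying a CRM-free status biases both failure rates down. On the at-12-months wording, a carried CRM-positive status could overcount, so the direction is settled only once the two wordings are reconciled. The order of LOCF and the no-diary rule is unstated, and no planned analysis tests the assumption about lost infants, not even the one that section 8.5 itself used in planning.

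The effect is modest. With equal loss the test keeps its level, and at 1/7 loss the shrinkage is about 2 to 4 points, well inside the sampling error. Rejection rates of 5.2-6.2% (half seen) or 7.5-11.7% (upper bound) rest on assumed unequal loss of 10% v 20-25%. The tipping example is fairly robust unless loss is informative. All these figures depend on assumed loss rates and on m; only the pilot losses come from the documents.

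**What to change.** 1. Reconcile the through-12-months and at-12-months wordings of the endpoint.
2. In the primary analysis, do not carry a CRM-free status forward as a 12-month success. Keep any failure seen before loss as a failure. Determine the status of the remaining infants from the monthly admission, medical-visit, medication and respiratory data already collected. One option is a simple multiple imputation with treatment arm, gestational-age stratum, cohort and, where numbers allow, site, which section 5.3 uses as a stratification factor. The O₂ challenge should enter only as a predictor.
3. State what lacking diary data means, which missing-data rule comes first, the order of the substitute sources, and the censoring rule for Kaplan-Meier/Cox.
4. Add a tipping-point analysis and an all-missing-as-failure analysis. Note that the latter also shrinks the risk difference and is a bound, not a better estimate for sizing.

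The cost is SAP wording, modest programming and slightly wider confidence intervals, with no new data. Which deaths count as failures is a separate matter for the sponsor to reconcile: the efficacy text in section 8.5 names respiratory deaths, while section 8.1 and the power analysis imply all deaths.

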9 ETHICAL CONSIDERATIONS

9.1 Informed Consent

Written informed consent must be obtained from the infant's parent or legal guardian prior to enrollment of the patient. The patient informed consent will be explained by the attending physician to the parent or guardian who must then sign the form which is included as Appendix B.

9.2 Institutional Review Boards

The study will be reviewed and approved by the Institutional Review Board (IRB) at each of the sites.

Copies of the IRB approval letters will be included as Appendix F.

10 DATA HANDLING, ANALYSIS AND RECORD KEEPING

All records pertaining to this trial will be retained by the Sponsor or participating institutions for FDA inspection. All used and unused drug vials must be accounted for and all used and unused vials must be returned to the Sponsor at the conclusion of the trial.

APPENDIX A: DEFINITIONS OF SPECIFIC ADVERSE EVENTS
CRITERIA FOR ADVERSE EVENTS ASSOCIATED WITH NOSOCOMIAL INFECTION,
AIR LEAKS AND PULMONARY HEMORRHAGE

1. Sepsis

A number of terms confuse the definition of sepsis, including infection, bacteremia, sepsis syndrome, and septic shock. For the purpose of this study, only the term sepsis should be used for AE reporting. Sepsis occurring in the first 3 days after birth (early onset) is considered congenital and should be recorded under past medical history, not as an AE. Sepsis will be defined as the systemic inflammatory response to infection, with criteria adapted from the Centers for Disease Control (CDC) Surveillance of Nosocomial Infection Control Program. All infants with suspected sepsis should have at least 2 sets of blood cultures from 2 separate sites, a urine culture and a cerebral spinal fluid (CSF) culture, with other cultures as determined by the investigator. If a central line is in place, one blood culture should be drawn from the central line (if possible) and one peripherally. A diagnosis of sepsis will require meeting at least one clinical sign or symptom, one invention survey, and one therapy condition.

Definition of nosocomial sepsis

Clinical signs/symptoms Criteria- must meet at least one

Lethargy

Fever ($>38^{\circ}\text{C}$), hypothermia ($<37^{\circ}\text{C}$) or temperature instability

Apnea (increase in frequency and severity from baseline)

Bradycardia (<100 beats/min) or tachycardia (>170 beats/min) (increase frequency and severity from baseline)

Hypotension (mean bp > 10 mm hg below the gestational age with capillary refill time > 5 secs and/or metabolic acidosis on a blood gas)

Oliguria (<1 ml/kg/hour over a 12 hour period)

Infection survey Criterion – must meet

No apparent infection or alternative cause at another site

Therapy Criterion – must meet

Anti-infective drugs given for ≥ 4 days

While all cases meeting the definition of nosocomial sepsis must be recorded as AEs, additional information will be collected on each episode to permit classification of the diagnosis into definite, probable, and no agent identified. Criteria for confirmation of a case of definite sepsis require microbiologic confirmation of an infecting organism. All cases of definite sepsis must meet one of the

criteria defined above. In addition to meeting the definition of nosocomial sepsis, cases of probable sepsis will have one positive blood culture for coagulase negative staphylococcus.

Criteria for the confirmation of a diagnosis of definite sepsis

One blood culture positive for all bacterial, viral, and fungal pathogens other than coagulase negative staphylococcus.

Two positive blood cultures coagulase negative staphylococcus

One positive blood culture and one culture from an otherwise sterile site (CSF, joint, pleural, or peritoneal fluid, bone or deep tissue abscess material) Coagulase negative staphylococcus; urine is excluded as a sterile site unless from a suprapubic tap

Nucleic acid testing, Latex fixation, or PCR assay

Diagnostic single-antibody titer (IgM) or 4-fold increase in paired sera (IgG) for pathogen

2. Pneumonia

Although pneumonia is an important nosocomial infection in the NICU, the diagnosis is often difficult to make due to the inadequacies of current diagnostic methods. For the current trial, pneumonia will be more rigorously defined according to the Centers for Disease Control prevention algorithm. Pneumonia occurring in the first 3 days after birth (early onset) is considered congenital and should be recoded under past medical history, not as an AE. All AEs of pneumonia must meet at least one radiographic, one gas exchange, and 3 clinical or vital signs criteria listed below. **Respiratory manifestations not meeting these criteria should be listed by an alternative etiology (i.e. pneumothorax, aspiration, sepsis, etc.) or by symptom (i.e. apnea, bradycardia).**

Definition of nosocomial pneumonia

Radiographic Criteria – must meet at least one

Persistent new or progressive infiltrate consistent with infection (interstitial, bronchial, or alveolar)

Consolidation

Cavitation

Abscess

Pneumatocele

Gas exchange Criteria – must meet at least one

Oxygen desaturation episodes (increased in frequency and severity from baseline)

Increased oxygen requirement of at least 10 percentage points

Increased ventilation requirement

Clinical/vital signs Criteria – must meet at least 3

Cough

Wheezing, rales or rhonchi

Apnea, tachypnea, nasal flaring with retraction of chest wall, or grunting

New onset of lower respiratory tract secretions, change in character of secretions, or increase in the quantity of secretions or suctioning requirements

Temperature instability

Bradycardia (<100 beats/min) or tachycardia (>170 beats/min)

While all cases meeting the definition of nosocomial pneumonia must be recorded as AEs, additional information will also be collected on each pneumonia episode to permit classification of the diagnosis into probable or definite pneumonia. Criteria for confirmation of a case of definite pneumonia require microbiologic confirmation of an infecting organism. All cases of definite pneumonia must meet one of the criteria defined below.

Criteria for the confirmation of a diagnosis of pneumonia – must meet at least one

Endotracheal aspiration $\geq 10^6$ cfu/ml

Bronchoscopy with BAL $\geq 10^4$ cfu/ml

Positive blood culture for a respiratory tract pathogen

Positive pleural fluid cultures

Isolation of virus or detection of viral antigen in respiratory secretions

Diagnostic single-antibody titer (IgM) or 4-fold increase in paired sera (IgG) for pathogen

Histopathologic evidence of pneumonia

PCR or other genomic identification of respiratory pathogen from lower respiratory tract specimen

3. Air leaks

The group of AEs comprising “air leaks”, and including pneumothorax, pulmonary interstitial emphysema (PIE), and pneumomediastinum, are typically related AEs and often occur in the same patient. Pneumothorax occurs when air collects in the pleural space between the lung and chest wall and can make breathing difficult. PIE occurs in connection with pneumothorax and is detected by radiologic imaging of the lungs. Pneumomediastinum occurs when air leaks into the mediastinum, putting pressure on the heart and lungs.

Pneumothorax

Definitive diagnostic criteria for pneumothorax include increased requirement for respiratory support and chest X-ray showing free air in the chest, collapsed lung and/or displacement of the heart and mediastinum. The most serious cases of pneumothorax require a chest tube to alleviate the pressure on the affected lung.

PIE

PIE is diagnosed radiologically and appears as small round, oval, and/or linear pulmonary lucencies which may be focal or diffuse. Lung volumes are increased and the heart size decreases as intrathoracic pressure increases. If subpleural cysts rupture, PIE potentially may lead to pneumothorax, pneumomediastinum, or even pneumopericardium.

Criteria for the confirmation of a diagnosis of PIE. Confirmation of a diagnosis of PIE is made by a second neonatal radiologist who concurs with the positive diagnosis.

Pneumomediastinum

Pneumomediastinum is confirmed radiologically when a radiolucent outline around the heart and mediastinum is observed in the thoracic cavity.

Air leaks can be life-threatening. For purposes of this study, all air leak AEs will be reported as SAEs and followed closely.

4. Pulmonary Hemorrhage

Pulmonary hemorrhage occurs when blood leaks into the lungs of infants in respiratory distress. It is diagnosed by an increased requirement for respiratory support, bradycardia, drop in blood pressure, and is often associated with patent ductus arteriosis (PDA). Severe pulmonary hemorrhage is treated with increasing end expiratory pressure and supportive blood transfusions. This condition can be life-threatening and will be reported as a SAE.

Therabron Therapeutics, Inc. (formerly Clarassance, Inc.)

Clinical Protocol

Recombinant CC10 Protein

